There are institutional processes to ensure that all persons assisting with the protocol will be well informed. The research personnel will conduct regular meetings and department email updates to review the results and safety data of the study. The research personnel will initiate the formation of a safety monitoring board for adverse effects, complications, or complaints from patient subjects.

 Mount Sinai	Protocol Title:	COMPARISON OF THE ANALGESIC EFFICACY OF A SINGLE SHOT INTERSCALENE BLOCK WITH LIPOSOMAL BUPIVACAINE TO BUPIVACAINE WITH DEXAMETHASONE AS AN ADJUVANT-A RANDOMIZED CONTROLLED TRIAL
	Principal Investigator Name/Contact Info:	[name] MD. [name] [name]. [name] MD, PHD [name] MD [contact]
	Primary Contact Name/Contact Info	[name] MD. [contact]
	Date Revised:	
	Study Number:	

5) Study Design

Prospective triple blinded randomized control trial.

With the HIPAA waiver requested, the surgeon will provide the investigators (both of them are physicians within the Department of Anesthesiology) with information of eligible patients. Subjects will be called by the department of Anesthesiology when their surgery is scheduled, and they will be introduced about the study then. The surgeons will also introduce the study to the patients in their office. All patients will be provided with copies of the IRB protocol and consent if they wish to have it. Copy of the consent form will be sent in a secured email to the potential subject. The email will be secured by entering in [SECURE] in the e-mail subject line. All patients scheduled to undergo total shoulder repair will be approached and recruited.

On the day of the surgery, the team will finalize participation and ask the subject to sign study consent forms. The study will not be introduced to the patients on the day of the surgery.

Once the anesthesiologist team performs a thorough pre operative evaluation, an intravenous catheter will be placed for administering medications.

After placement of standard ASA monitors and 4mg of midazolam as sedation all patients will receive single shot interscalene block performed by residents under direct supervision of regional anesthesiology attending with the help of ultrasound guidance.

 Mount Sinai	Protocol Title:	COMPARISON OF THE ANALGESIC EFFICACY OF A SINGLE SHOT INTERSCALENE BLOCK WITH LIPOSOMAL BUPIVACAINE TO BUPIVACAINE WITH DEXAMETHASONE AS AN ADJUVANT-A RANDOMIZED CONTROLLED TRIAL
	Principal Investigator Name/Contact Info:	[name] MD. [name] [name]. [name] MD, PHD [name] MD [contact]
	Primary Contact Name/Contact Info	[name] MD. [contact]
	Date Revised:	
	Study Number:	

patients will be randomized using computer generated tables and sealed envelopes. A designated resident not involved in the study will open the sealed envelope and randomize the patient into the following groups:

Group A—Liposomal bupivacaine(133mg bupivacaine diluted normal saline total 25cc)

Group B---Dexamethasone 4mg in 0.5% Bupivacaine 25cc

The patients will be transferred to the OR to proceed with the surgery. Standard ASA monitors will be placed again and after pre oxygenation, general anesthesia will be induced with propofol and fentanyl. Laryngeal mask airway of appropriate size will be inserted and patient will be connected to the ventilator for the procedure. Maintenance of anesthesia will be achieved with sevoflurane and oxygen/air mixture. Once the procedure is completed, patients will be extubated and transferred to the recovery room(PACU) for post anesthetic care.

The patient will also receive 4mg of ondansetron intra-venous in the OR as prophylaxis for post operative nausea and vomiting.

Patients, attending anesthesiologists, surgeon and research assistant collecting the data will be blinded of the group assignment. The medication solution will be prepared by the resident physician.

 Mount Sinai	Protocol Title:	COMPARISON OF THE ANALGESIC EFFICACY OF A SINGLE SHOT INTERSCALENE BLOCK WITH LIPOSOMAL BUPIVACAINE TO BUPIVACAINE WITH DEXAMETHASONE AS AN ADJUVANT-A RANDOMIZED CONTROLLED TRIAL
	Principal Investigator Name/Contact Info:	[name] MD. [name] [name]. [name] MD, PHD [name] MD [contact]
	Primary Contact Name/Contact Info	[name] MD. [contact]
	Date Revised:	
	Study Number:	

Pain scores in the form of NRS (NUMERICAL RATING SCALE) will be assessed on arrival to PACU. Pain scores will also be assessed 1 hour after arrival to PACU and at the time of discharge from PACU. NRS scores will be assessed on the floors every 6 hourly during the first 24 hours, 8 hourly and then every 12 hourly during the second 24 hours. If NRS scores are more than 5 at any time a one-time dose of oxycodone 10mg and Tylenol 1000 mg will be given.

Once the primary team discharges the patient, a telephone follow - up every day until resolution of any residual arm weakness/numbness will be done by the anesthesia resident originally involved in the surgery.

Patients will also be asked to note the time to first analgesic request in addition to onset of sensory discomfort and motor recovery.

a) Recruitment Methods

See above. With the HIPAA waiver requested, the surgeon will provide investigators (both of whom are physicians within the department of Anesthesiology) with information of eligible patients. After the operating room schedule has been reviewed for potential participants in the study the contact information will be obtained through the surgeon's office. Subjects will be called by the department of Anesthesiology when their surgery is scheduled, and they will be informed about the study then.

 Mount Sinai	Protocol Title:	COMPARISON OF THE ANALGESIC EFFICACY OF A SINGLE SHOT INTERSCALENE BLOCK WITH LIPOSOMAL BUPIVACAINE TO BUPIVACAINE WITH DEXAMETHASONE AS AN ADJUVANT-A RANDOMIZED CONTROLLED TRIAL
	Principal Investigator Name/Contact Info:	[name] MD. [name] [name]. [name] MD, PHD [name] MD [contact]
	Primary Contact Name/Contact Info	[name] MD. [contact]
	Date Revised:	
	Study Number:	

b) Inclusion and Exclusion Criteria

Inclusion criteria: All patients between age 18-75 years undergoing primary shoulder arthroscopic procedure. All patients who speak read and understand English will be included for follow up purposes.

Exclusion criteria included patients with patient refusal, ASA 5, presence of coagulopathy, severe lung disease, contralateral diaphragmatic palsy, insulin-dependent diabetes, hepatic disease/failure, kidney disease/failure, pregnancy, chronic opioid use (defined as opioid use for >3 months), or allergy to any of the study medications.

c) Number of Subjects

N= 100, recruit ability is manageable. Based on previous study conducted by Tandoc et al with estimated average duration of analgesia at 22 hours with dexamethasone in 0.5% bupivacaine and assumed average SD of 3 hours, they estimated that 16 patients would be needed to provide 80% power to conclude absence of effect at the significance level of 0.05 among treatment groups. To allow for 20% patient dropouts, 30 subjects per group will be targeted for enrollment.

Data will be expressed as mean \pm SD or median with interquartile range as appropriate. Categorical data will be analyzed with Fisher exact test and chi-square test. The duration of analgesia and motor block will be analyzed by the Kaplan-Meier survival analysis and Cox

 Mount Sinai	Protocol Title:	COMPARISON OF THE ANALGESIC EFFICACY OF A SINGLE SHOT INTERSCALENE BLOCK WITH LIPOSOMAL BUPIVACAINE TO BUPIVACAINE WITH DEXAMETHASONE AS AN ADJUVANT-A RANDOMIZED CONTROLLED TRIAL
	Principal Investigator Name/Contact Info:	[name] MD. [name] [name]. [name] MD, PHD [name] MD [contact]
	Primary Contact Name/Contact Info	[name] MD. [contact]
	Date Revised:	
	Study Number:	

proportional hazards modeling. Subgroup pairwise analyses will be conducted via Kruskal-Wallis rank test with Bonferroni correction for significance. All analysis will be conducted with intent-to-treat approach to minimize the potential effects of dropout. Statistical significance will be defined as $P<0.05$.

d) Study Timelines

2018-2019 and subsequent data analysis. The subject's participation will be from time of enrollment to complete resolution of arm weakness and motor strength. Estimated date of enrollment completion will be when 100 eligible subjects are enrolled in final data analysis. Estimate date for study completion will be June 2019.

e) Study Endpoints

Primary end point will be the time of first analgesic request for the first 24 hours post operatively.

Secondary end points will be NRS at 6 hours, 12 hours, 18 hours, 24 hours, 36 hours and 48 hours and oxycodone use.

f) Procedures Involved in the Human Research

Prospective randomized controlled trial and data analysis only.
Ultrasound guided interscalene block with nerve catheter placement.

 Mount Sinai	Protocol Title:	COMPARISON OF THE ANALGESIC EFFICACY OF A SINGLE SHOT INTERSCALENE BLOCK WITH LIPOSOMAL BUPIVACAINE TO BUPIVACAINE WITH DEXAMETHASONE AS AN ADJUVANT-A RANDOMIZED CONTROLLED TRIAL
	Principal Investigator Name/Contact Info:	[name] MD. [name] [name]. [name] MD, PHD [name] MD [contact]
	Primary Contact Name/Contact Info	[name] MD. [contact]
	Date Revised:	
	Study Number:	

g) Specimen Banking

N/A

h) Data Management and Confidentiality

Data collected in excel file to be de-identified after initial collection. Excel file be subsequently encrypted and shared only between the two above listed investigators via secure Mt. Sinai (chpnet) electronic mail.

The information included in the data will be medical record number, age, gender, ASA class, type of surgery, pain score assessments, duration of surgery, anesthesia time, time to first narcotic, total narcotic use and pain scores up to 48 hours after surgery. In case of known history of type 1 or 2 diabetes, preoperative and post operative finger stick will be recorded. Time of administration of study drug, smoking status and patient satisfaction scores will also be recorded. Only the research personnel will have access to the data. The data will be stored as a hard copy files and on a secure spreadsheet. The research personnel are responsible for the receipt of the data. The PI will keep the hard copies secure and any electronic data will be encrypted. No personal identifiers will be used. The data will undergo statistical analysis.

i) Provisions to Monitor the Data to Ensure the Safety of subjects

 Mount Sinai	Protocol Title:	COMPARISON OF THE ANALGESIC EFFICACY OF A SINGLE SHOT INTERSCALENE BLOCK WITH LIPOSOMAL BUPIVACAINE TO BUPIVACAINE WITH DEXAMETHASONE AS AN ADJUVANT-A RANDOMIZED CONTROLLED TRIAL
	Principal Investigator Name/Contact Info:	[name] MD. [name] [name]. [name] MD, PHD [name] MD [contact]
	Primary Contact Name/Contact Info	[name] MD. [contact]
	Date Revised:	
	Study Number:	

Part I: Elements of Data and Safety Monitoring Plan

MSSM Principal Monitor:

Last Name: [name]

First Name: [name]

Academic Title: Attending Physician, Professor

Department: Anesthesiology

Mailing Address: Mount Sinai West [name]

[contact]

Fax:

E-mail: [contact]

MSSM Principal Monitor:

Last Name: [name]

First Name: [name]

Academic Title: Attending Physician, Assistant Professor

Department: Anesthesiology

Mailing Address: Mount Sinai West [name]

[contact]

Fax:

E-mail: [contact]

Last Name: [name]

First Name: [name]

Academic Title: Attending Physician, Professor

Department: Orthopedics

Mailing Address: Mount Sinai West [name]

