 Mount Sinai	Protocol Title:	COMPARISON OF THE ANALGESIC EFFICACY OF A SINGLE SHOT INTERSCALENE BLOCK WITH LIPOSOMAL BUPIVACAINE TO BUPIVACAINE WITH DEXAMETHASONE AS AN ADJUVANT-A RANDOMIZED CONTROLLED TRIAL
	Principal Investigator Name/Contact Info:	[name] MD. [name] [name]. [name] MD, PHD [name] MD [contact]
	Primary Contact Name/Contact Info	[name] MD. [contact]
	Date Revised:	
	Study Number:	

part of anti- emetic prophylaxis and anti inflammatory effect. Methyl prednisone was the first steroid to be used as an adjuvant. Dexamethasone was first used as an adjuvant in 2003.

It has been hypothesized that steroids induce a degree of vasoconstriction, thereby reducing local anesthetic absorption, tend to have an opioid sparing effect. Another theory suggests that it increases the activity of inhibitory potassium channels on nociceptive C-fibers (via glucocorticoid receptors), thus decreasing their activity.

Several studies have demonstrated promising results with the use of 8mg of perineural dexamethasone. No neuronal injury has been reported in in vivo studies. Though there are several studies which report usage of dexamethasone in varying doses of 2mg to 8mg, the optimal effective dose of dexamethasone as an adjuvant for nerve block remains unknown. Some studies have suggested perineural is more effective than IV as an adjuvant. Hence we propose to study the lowest effective dose of dexamethasone as an adjuvant which can be used as an adjuvant to local anesthesia in interscalene block for shoulder surgeries.

Liposomal bupivacaine, a formulation where bupivacaine is encapsulated into multivesicular liposomes, making it a slow and controlled release from the liposomes, was originally indicated for wound infiltration at the surgical site to provide post surgical analgesia. Studies have demonstrated efficacy upto 24 hours in femoral nerve block in total knee arthroplasty. Recent approval of liposomal bupivacaine in interscalene block for shoulder surgeries by FDA opens an arena unexplored in the world of regional anesthesia.

 Mount Sinai	Protocol Title:	COMPARISON OF THE ANALGESIC EFFICACY OF A SINGLE SHOT INTERSCALENE BLOCK WITH LIPOSOMAL BUPIVACAINE TO BUPIVACAINE WITH DEXAMETHASONE AS AN ADJUVANT-A RANDOMIZED CONTROLLED TRIAL
	Principal Investigator Name/Contact Info:	[name] MD. [name] [name]. [name] MD, PHD [name] MD [contact]
	Primary Contact Name/Contact Info	[name] MD. [contact]

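### The supervising attending is listed as blinded but is present at every injection, and the two solutions are matched only for volume with no masking of syringe or tubing described

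*Combined protocol and SAP*

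**What the plan says.** Section 5) Study Design of the combined protocol and SAP describes the trial as a "Prospective triple blinded randomized control trial" and names four blinded roles: "Patients, attending anesthesiologists, surgeon and research assistant collecting the data will be blinded of the group assignment". Residents are not on that list.

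The same section describes the block as "single shot interscalene block performed by residents under direct supervision of regional anesthesiology attending", under ultrasound guidance.

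The two preparations are given as "Group A—Liposomal bupivacaine(133mg bupivacaine diluted normal saline total 25cc" and "Group B---Dexamethasone 4mg in 0.5% Bupivacaine 25cc". The Brief Summary of Research describes the liposomal product as "a formulation where bupivacaine is encapsulated into multivesicular liposomes".

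On concealment, section 5 provides computer-generated randomization and sealed envelopes opened by a resident who is not involved in the study. It says that a resident physician prepares the solution, without saying whether this is the same person. Section 19, on control of drugs, is marked not applicable.

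**The concern.** A role declared blinded is placed where the study drug is injected, and the plan gives no means of keeping the blind there. Equal volume hides nothing about the look of a fluid. One product is a liposome formulation and the other is dexamethasone in plain bupivacaine, so a visible difference is plausible.

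If the supervising attending learns the arm, that knowledge could affect later decisions in the attending's hands. Intra-operative narcotic consumption is a listed secondary outcome (section 1). Section 5 names fentanyl at induction without giving an amount or a criterion, so on the text there is discretion. There is also a reporting issue: a paper calling the trial triple blinded, with attendings among the blinded, would claim something the written procedure does not secure.

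**Working it through.** No alpha, power or sample-size figure bears on this point, and the plan gives no figure for blinding to reproduce. The check sets the passages side by side.

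1. **Who is meant to be blinded.** Four roles: patient, attending anesthesiologist, surgeon, data-collecting research assistant (section 5).
2. **Who is at the injection.** The resident performing the block and the directly supervising regional attending (section 5). Of these two, only the attending is on the blinded list. The resident's view of the syringe contradicts nothing.
3. **What is matched.** Both arms are given as 25cc. Even this is slightly loose: Group A is stated as a total, while Group B does not say whether 25cc includes the dexamethasone. No other matching is described.
4. **What differs.** Group A contains multivesicular liposomes in saline; Group B does not. The appearance of either fluid is not stated. *Assumption:* a liposome suspension can be told by eye from dexamethasone in plain bupivacaine.
5. **What safeguards exist.** Sealed envelopes and an uninvolved opener conceal the allocation before assignment. They do not cover the syringe afterwards. The available text mentions no opaque syringe or tubing, screen, pharmacy preparation, separate unblinded block team or check of the blind.
6. **Result.** Under the assumption in step 4, one of the four listed roles is exposed at each block. The route does not reach the other three: patients receive midazolam before the block, and neither the surgeon nor the research assistant is placed at the injection.
7. **Reach to outcomes.**
   - *Intra-operative narcotic (secondary):* exposed if the block attending also runs the anesthetic. The plan neither requires nor forbids this.
   - *Time to first analgesic request:* section 5 ties oxycodone and Tylenol to an NRS score above 5 and has patients note the time of first request themselves. Number of Subjects (section 5c) assumes mean analgesia of 22 hours and SD 3 hours with dexamethasone in 0.5% bupivacaine. If durations are roughly normal, a first request by 6 hours lies (22 − 6)/3 = 5.3 SD below the mean, and by 12 hours (22 − 12)/3 = 3.3 SD below. The 6- and 12-hour cut-offs are illustrative. On these figures, behaviour by the attending in early recovery would seldom determine the endpoint in Group B. No duration is given for Group A.

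**The case against.** The strongest reply is that the deciding fact is not in the documents. Neither fluid's appearance is described, nothing says the syringe is in plain view, and section 5 does require the attending to be blinded, so a site following it would have to mask somehow. On that view the gap is one of description. Part of this stands: the visible difference must remain a labelled assumption. But the plan assigns a blind to someone overseeing the injection and gives no step that would achieve it, while the steps it does give would leave that person exposed if the fluids differ. If they look alike, one sentence saying so would settle the matter. Two short stretches of the document, adjoining the personnel and safety-monitoring text, were not available, so a masking provision there cannot be fully excluded.

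Three stronger readings are tempting, and the documents do not support them:

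- *That the triple blind fails as a whole.* Only one of four listed roles is shown to be at risk; three remain.
- *That the arm is revealed in all 100 planned patients.* That figure is the appearance assumption multiplied by the sample size and adds no evidence. Section 5c also gives a target of 30 per group, so the number itself is unsettled.
- *That the primary result is biased.* The score-based trigger, patient-noted request time and assumed 22-hour duration make the route indirect. NRS and satisfaction come from patients, whose blind is not challenged here.

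A separate exposure may be better documented: after discharge, the anesthesia resident originally involved in the surgery makes the daily calls about weakness and numbness. That role is not listed as blinded, so it is no contradiction of the list, but it belongs in any honest account of who was blinded.

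**Conclusion.** The point holds in limited form. The plan lists attending anesthesiologists as blinded, has one directly supervise each injection, and matches the solutions on volume alone without any described masking. Assuming the fluids can be told apart by eye, the blind as stated does not hold for the supervising attending.

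The consequence is modest. The exposed outcome is one secondary item, intra-operative narcotic consumption, and only where the block attending also gives the anesthetic. The documents allow no estimate of its size, nor of any indirect effect on time to first analgesic request. The change is still worth making because it is cheap and because the blinding claim would otherwise go beyond what the written procedure supports.

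**What to change.** In section 5, have the uninvolved resident who opens the envelope also prepare the 25cc and hand it over in identical syringes with opaque sleeves and opaque extension tubing. State whether 25cc is the total volume in both arms.

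If this is not done, remove the block attending from the blinded list and, in the report, name exactly which roles were blinded and how, instead of using the label triple blinded. The same applies if enrolment has already ended, which is possible: the document is dated June 2021 and Study Timelines (section 5d) estimated completion in June 2019.

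The cost is the sleeves and tubing covers plus about two sentences of protocol text. A short visible segment may remain for aspiration, so masking may be incomplete and should be described that way. A rule that anyone who saw the syringe takes no part in later analgesic decisions would be stricter, but it could require a second attending and is not needed for the correction.

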	Date Revised:	
	Study Number:	

Based on the above two options in the current opioid epidemic crisis, we propose to study the analgesic efficacy of liposomal bupivacaine to bupivacaine with dexamethasone as an adjuvant in interscalene block for shoulder surgeries. Till date, there is not study comparing the two.

1) Objectives:

Research Question:

Is the analgesic efficacy of liposomal bupivacaine superior to that of bupivacaine with dexamethasone as an adjuvant in interscalene block?

Primary Outcome: The primary outcomes is the time of analgesia duration (defined as the onset of sensory discomfort that required medication) and time of motor recovery (defined as the recovery of full motor function of both wrist and elbow on the nerve block side). Time to first analgesic request, NRS at 6 hours, 12 hours, 24 hours and 48 hours, POD 3, 4, 5, 6, 7 and total narcotic consumption.

Secondary Outcome: arm weakness (0 to 24 hours, 24 to 48 hours), arm numbness (0 to 24 hours, 24 to 48 hours), nausea, vomiting, dizziness, Horner's syndrome, hoarseness, dyspnea, Intra operative narcotic consumption, PACU and hospital length of stay, pain scores as assessed by PT on POD 1, and 2.

 Mount Sinai	Protocol Title:	COMPARISON OF THE ANALGESIC EFFICACY OF A SINGLE SHOT INTERSCALENE BLOCK WITH LIPOSOMAL BUPIVACAINE TO BUPIVACAINE WITH DEXAMETHASONE AS AN ADJUVANT-A RANDOMIZED CONTROLLED TRIAL
	Principal Investigator Name/Contact Info:	[name] MD. [name] [name]. [name] MD, PHD [name] MD [contact]
	Primary Contact Name/Contact Info	[name] MD. [contact]
	Date Revised:	
	Study Number:	

patient's satisfaction scores(Yes- I would prefer the same analgesic technique the next time or No-I would prefer a different analgesic technique) and quality of sleep (good, moderate/average, bad) on POD 0 and 1. Patient reported outcomes measurement information system (PROMIS) baseline global assessment will be conducted prior to surgery and post operative pain assessment at first follow up visit. Each patient will be assessed by standardized assessment of shoulder function as recommended by American association of shoulder and elbow surgery.

2) Background

See above. There have been several studies demonstrating efficacy of dexamethasone in prolonging the analgesic effect when administered both perineurally and intra-venously as an adjuvant to local anesthesia demonstrating a dose effect relationship.

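### No NRS is scheduled before the block and no baseline-adjusted NRS analysis is specified, so a cheap but uncertain precision gain on the NRS endpoints is forgone

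*Combined protocol and SAP*

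**What the plan says.** Section 5 (Study Design) places the first pain score after the operation: "Pain scores in the form of NRS (NUMERICAL RATING SCALE) will be assessed on arrival to PACU". Further scores follow one hour later, at PACU discharge and on the floor. The steps before the block begin "Once the anesthesiologist team performs a thorough pre operative evaluation, an intravenous catheter will be placed for administering medications"; monitors, sedation and the block come next. None of these steps includes a pain score.

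Section 5e gives the NRS comparisons as "Secondary end points will be NRS at 6 hours, 12 hours, 18 hours, 24 hours, 36 hours and 48 hours and oxycodone use", alongside "Primary end point will be the time of first analgesic request for the first 24 hours post operatively". Section 1 (Objectives) instead lists under Primary Outcome "NRS at 6 hours, 12 hours, 24 hours and 48 hours, POD 3, 4, 5, 6, 7 and total narcotic consumption".

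Two other patient assessments appear in section 1. A PROMIS "baseline global assessment will be conducted prior to surgery and post operative pain assessment at first follow up visit". Also, "Each patient will be assessed by standardized assessment of shoulder function", with no timing stated. Neither is described as a pain baseline or tied to the NRS analysis.

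The data list in 5h has a generic entry for pain scores and another for scores up to 48 hours after surgery, but names no preoperative score. The analysis paragraph in 5c covers descriptive summaries, categorical tests, Kaplan-Meier and Cox methods for the durations, and a Kruskal-Wallis test for subgroup pairwise comparisons. It gives no model for NRS and no covariate.

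**The concern.** Patients come to shoulder surgery with differing amounts of pain. Chronic opioid users are excluded in 5b, but patients in pain are not, and section 5 describes no stratification of the randomisation by pain. If preoperative pain predicts postoperative NRS, that between-patient variation stays in the error term of every NRS comparison. A pre-treatment covariate could remove part of it without introducing bias. The measurement has to be taken before the block, because it cannot be recovered afterwards. At stake is the width of the confidence intervals for the NRS differences, not their validity.

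**Working it through.** **The plan's own figure.** There is none to reproduce for NRS. The 80% power statement in 5c concerns duration of analgesia, with an SD of 3 hours. No SD, target difference or power is given for NRS.

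**Inputs from the documents.** 5c gives both 30 per group and a total of 100. The total is taken here as 50 per arm, assuming equal allocation. Both sizes are shown, and the mismatch between them is a separate matter.

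**Assumed inputs (not in the documents).** NRS SD = 2.5. Correlation r between preoperative and postoperative NRS = 0 to 0.5. A linear model is also assumed.

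**Formulas, with n per arm.**
- Unadjusted SE of the difference = 2.5 × √(2/n). For n = 50 this is 2.5 × √0.04 = 0.500; for n = 30 it is 2.5 × √0.0667 = 0.645.
- Adjusted SE = unadjusted SE × √(1 − r²).
- Net variance factor after paying for one covariate = (1 − r²) × (1 + 1/(2n − 5)).

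| r | Variance cut (r²) | SE, n = 50 | Net factor, n = 50 | SE, n = 30 | Net factor, n = 30 |
|---|---|---|---|---|---|
| 0 | 0% | 0.500 | 1.0105 | 0.645 | 1.0182 |
| 0.1 | 1% | 0.497 | 1.0004 | 0.642 | 1.0080 |
| 0.2 | 4% | 0.490 | 0.9701 | 0.632 | 0.9775 |
| 0.3 | 9% | 0.477 | 0.9196 | 0.616 | 0.9265 |
| 0.4 | 16% | 0.458 | 0.8488 | 0.592 | 0.8553 |
| 0.5 | 25% | 0.433 | 0.7579 | 0.559 | 0.7636 |

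The SE columns leave out the small cost of the covariate; the net factors include it.

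**Break-even.** The net factor falls below 1 when r² > 1/(2n − 4). For n = 50 that is 1/96, so r > 0.10. For n = 30 it is 1/56, so r > 0.13. At r = 0 the cost of adjusting is 1% to 2% of the variance.

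**Power, as illustration only.** A difference that had 80% power unadjusted would have 81.6% at r = 0.2, 83.6% at r = 0.3 and 89.9% at r = 0.5. The plan sets no power target for NRS.

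**Chance imbalance.** With SD 2.5 and 50 per arm, the baseline difference between arms has SD 0.50. At r = 0.4 it shifts the unadjusted NRS difference by 0.4 × 0.50 = 0.20 (one SD). Removing that component gives 0.50² − 0.20² = 0.21, and √0.21 = 0.458, which is the adjusted SE in the table. The imbalance and the precision loss are therefore the same quantity.

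**Change score.** Its variance relative to the unadjusted comparison is 2(1 − r): 1.6 at r = 0.2, 1.4 at r = 0.3 and 1.0 at r = 0.5. Below r = 0.5 it is worse than using no baseline.

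**The case against.** The strongest reply is that nothing here is wrong. Randomisation protects the unadjusted comparison, and 5e makes NRS secondary. The size of the gain depends wholly on an SD and a correlation that the documents do not supply. All of that stands.

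The correlation may also be weak. 5c cites an average analgesia duration of 22 hours for dexamethasone in bupivacaine, and three of the six 5e time points (6, 12 and 18 hours) fall before that. Scores may then lie near zero, where the linear approximation is also poor. Later, section 5 gives rescue analgesia when NRS exceeds 5, which could loosen the link with preoperative pain. The upper end of the range is therefore unsupported.

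A further reply is that 5c names no method for comparing NRS between arms, so a baseline measurement alone would buy nothing. That is right, and it is why the analysis sentence is needed along with the measurement.

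A reader might infer three stronger points, none of which the documents support:
- **That the NRS comparisons are biased, or that a known amount of precision is certainly lost.** Allocation is randomised, and r is not given.
- **That a chance baseline imbalance is a second harm.** It is already inside the unadjusted SE and its confidence interval, as the arithmetic shows.
- **That nothing usable is collected before surgery.** The PROMIS baseline is planned. Its content is not described, so whether it captures pain cannot be settled here, but a covariate need not be on the outcome's scale.

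What survives the reply is that neither a pre-block NRS nor an adjusted analysis is written down, and that adding both costs very little.

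**Conclusion.** The point holds as a low-priority efficiency improvement. Precision on the NRS endpoints could improve by about r² of the variance. That means no gain below r of about 0.10 to 0.13, little at r = 0.2 to 0.3 (4% to 9%), and a material gain only near r = 0.5 (25%). The standard errors rest on an assumed SD of 2.5; the percentage reductions do not. The importance is limited by the secondary status of NRS in 5e, although section 1 lists NRS under Primary Outcome and the two sections need reconciling separately. Two stretches of the document were not available (within section 4, and between the monitoring plan in 5i and the text before section 7), so the absence of a pre-block NRS is established only for the rest.

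**What to change.** - **Section 5:** record one NRS for the surgical shoulder at the preoperative evaluation, before midazolam and the block.
- **Section 5h:** add this score to the data list.
- **Section 5c:** state that NRS at each time point will be compared between arms with the preoperative NRS as a covariate, in ANCOVA or a repeated-measures model and not as a change score. Report the adjusted difference with its 95% CI. State that a missing baseline will be set to the overall mean across both arms.
- **Fallback:** name the PROMIS baseline global assessment as a possible covariate where no preoperative NRS exists, including for any patient already treated.

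The cost is one question at a contact that already takes place, one spreadsheet column, a short addition to the analysis text and simple imputation of a few missing values. If the correlation proves negligible, adjustment costs about 1% to 2% of the variance.
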